- 9.1.13 **H5:** GBC+PIPT will have less transition to chronic LBP and will be more effective than GBC alone for improving functional outcomes and reducing LBP-related medical resource utilization for the subgroup of patients who are underserved or with depression. Because the interventions being studied do not specifically target obesity and smoking, and the relationship of these variables to transition to chronic are unclear, group x obesity interactions are not expected.
- 9.1.14 Outcomes for this aim will utilize the same measures and sources as PA1-2, SA3 but will also include EMR data on patient co-morbidities, smoking status, and socioeconomic status.
- 9.1.15 **Missing data:** Baseline characteristics, such as age, gender, and health insurance status, will be compared between patients with complete assessment data to those with missing data by treatment group in order to assess potential biases that may exist in the complete case analysis. Sensitivity analyses for the primary and secondary outcomes will be conducted using several methods, which have different missing data assumptions.
- 1) Complete case analyses, which assumes missing data are completely at random,
  - 2) Multiple imputation using M=10 imputations, which assumes missing at random, and
  - 3) Assigning poor scores and good scores for missing values differentially by treatment group, which aligns with non-ignorable missingness (the data missingness is nonrandom and related to the actual value).

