## 9.2 Randomization, sample size and power – RCT cohort

- 9.2.1 **Randomization** will occur at the clinic level, which was chosen for the pragmatic reason that randomizing patients within a clinic would result in cross contamination of the interventions within the same clinic. The biostatisticians and the individuals conducting the 6-month assessments will be blinded to the randomization assignment to avoid bias in analyses and data capture.
- 9.2.2 **Sample size** is based on the first primary outcome of the transition rate to chronic LBP at month 6. We propose to enroll N=1860 high risk acute LBP patients. We are targeting an average of n=31 enrolled high risk patients per clinic ( $60 \times 31 = 1860$ ) to account for the variation in cluster sizes (assuming coefficient of variation=0.65) and 40% non-response rate at 6 months.
- 9.2.3 **Power:** With a total of 60 PCP clinics for randomization, m=30 clinics per intervention strategy and fixed n=10-14 completers per clinic for the 6-month assessment, we will have just over 80% power to detect a 40% reduction in transition to chronic LBP assuming the control arm has a transition rate of 25%-30% and the intraclass correlation is 0.05, which is an upper bound for what has been observed in other cluster randomized trials with respect to either pain or LBP. Assuming that low and medium risk subjects with acute LBP have an expected 20% transition to chronic and using data on obesity and smoking rates based on national surveys, depression rates based on prevalence rates reported in primary care, and proportions of underserved patients estimated from patient registries at each of the five regional sites, the planned sample size for the observational cohort is sufficient to detect at least a 30% relative difference (6% absolute difference) from 20% with powers ranging from 79% to 87%. The study would have 65% power to detect a 40% relative or 8% absolute difference (hypothesized increased rate of transition) for the depression subgroup.

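### The only non-ignorable missing-data analysis (9.1.15, item 3) is undefined and, on its natural reading for chronic LBP, gives bounds 80 points wide at the planned 40% non-response

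*Combined protocol and SAP*

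**What the plan says.** Section 9.1.15 (Missing data) states that "Sensitivity analyses for the primary and secondary outcomes will be conducted using several methods, which have different missing data assumptions". It lists three: a complete-case analysis, multiple imputation with ten imputations under missing at random, and "Assigning poor scores and good scores for missing values differentially by treatment group", which the plan ties to non-ignorable missingness. The third is the only one that lets missingness depend on the unseen outcome. The section also plans to compare baseline characteristics of patients with and without assessments, by arm.

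Nothing else in the document defines a poor or a good score, the direction by arm, whether both directions are run, the fraction of missing values assigned, or how the result is to be read.

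Section 9.2.2 sets the scale of the problem: "We propose to enroll N=1860 high risk acute LBP patients", with the sample size allowing for a "40% non-response rate at 6 months". Section 9.2.3 assumes a control transition rate of 25-30%, a 40% relative reduction and an intraclass correlation of 0.05. The first primary outcome is binary (3.3.1). The second, the Oswestry, is a score from 0 to 100 (3.3.2).

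**The concern.** With two patients in five expected to have no 6-month assessment, the assumption about those patients may matter more to the primary conclusion than anything else in the analysis. Item 3 is where the plan meets that risk.

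For a yes/no outcome, a poor score for a patient is chronic LBP and a good score is no chronic LBP. No value lies between unless the plan adds a fraction or a probability, and it adds none. Assigning opposite extremes to the two arms then produces best-case and worst-case bounds. At 40% missing, the width of those bounds is set by the missing fraction and not by what responders report. Readers would not learn how informative non-response would have to be to change the conclusion.

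**Working it through.** **Inputs.** 60 clinics, "m=30 clinics per intervention strategy", 31 enrolled per clinic (930 per arm), 40% non-response, cluster-size CV 0.65, ICC 0.05, control rate 25% or 30%, and a 40% relative reduction, so 15% or 18% under PIPT (9.2.2, 9.2.3). Three assumptions are mine: non-response is equal by arm; alpha is two-sided 0.05, which the plan states only for the observational cohort (Table 3); and assignment does not change the ICC.

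**The plan's own figure.** Section 9.2.3 claims "just over 80% power to detect a 40% reduction in transition to chronic LBP" with "fixed n=10-14 completers per clinic for the 6-month assessment". Take effective n per arm as 30n / [1 + (n - 1) × 0.05] and a pooled two-proportion test.
- 25% vs 15%, n = 14: 420 / 1.65 = 254.5, power 80.7%.
- 30% vs 18%, n = 10: 300 / 1.45 = 206.9, power 81.8%.

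The claim is reproduced, so the inputs are read as intended.

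**Extreme assignment, first primary outcome.** Arm rate = (1 - m) × responder rate + m × assigned value, with m = 0.4. Differences are PIPT minus GBC.

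| Responders (GBC vs PIPT) | Adverse to PIPT | Favourable to PIPT |
|---|---|---|
| 25% vs 15% | (0.09 + 0.40) - 0.15 = +34 points | 0.09 - (0.15 + 0.40) = -46 points |
| 30% vs 18% | (0.108 + 0.40) - 0.18 = +32.8 points | 0.108 - (0.18 + 0.40) = -47.2 points |

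The bounds are always 2 × 40 = 80 points apart.

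**When the adverse bound keeps its sign.** With responder reduction d, this needs (1 - m)d > m.
- At m = 0.4: d > 0.4 / 0.6 = 66.7 points, which cannot arise from a 25-30% control rate. Even with no chronic cases among PIPT responders and 30% in GBC, the adverse case is 40% vs 18%, or +22 points.
- Solved for m, the sign changes at m = d / (1 + d): 0.10 / 1.10 = 9.1% and 0.12 / 1.12 = 10.7%.
- At 20% missing, half the planned rate, the adverse bound is still +12 points (32% vs 20%) or +10.4 points (34.4% vs 24%).

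**Oswestry.** If non-responders are assigned means that differ by a gap g against PIPT, the sign holds only if the observed mean difference exceeds (0.4 / 0.6) × g. That is 3.3 points for g = 5, 6.7 for 10, 13.3 for 20 and 66.7 for 100. The plan gives no gap, SD or target difference, so no conclusion about reversal follows.

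**What a graded analysis would show.** Hold GBC non-responders at the GBC responder rate and let PIPT non-responders have rate q. The effective n per arm lies between two values:
- completers only: design effect 1 + [(0.65² + 1) × 18.6 - 1] × 0.05 = 2.27, so 558 / 2.27 = 245.5;
- all enrolled, with imputed values treated as observed: the same formula with 31 gives 3.15, so 930 / 3.15 = 294.8.

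With 25% vs 15% and a pooled z-test:
- The PIPT rate overall is 0.6 × 0.15 + 0.4q. The z value falls to 1.96 at q = 21.9% (n = 245.5) or 23.4% (n = 294.8). Against PIPT responders these are odds ratios of 1.59 and 1.73.
- The effect is zero when 0.09 + 0.4q = 0.25, so q = 40%, an odds ratio of (0.40 / 0.60) / (0.15 / 0.85) = 3.78.

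With 30% vs 18%, significance is lost at q = 28.6% to 30.2% (odds ratios 1.82 to 1.97). The effect is zero at q = 48% (odds ratio 4.21).

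**The case against.** The strongest reply is that section 9.1.15 never says the assignment is all-or-nothing. A fractional or graded assignment by arm fits the same words, and it would have a usable tipping point: the effect reaches zero when the rate among PIPT non-responders is 15 points (25% case) or 18 points (30% case) above that among GBC non-responders. This stands as a caution about the reading. It does not rescue the plan, because no graded rule is written down and the only non-ignorable analysis would then be chosen after the data are seen.

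A reader might infer that item 3 is certain to overturn any result. The documents do not support that. Only the adverse direction reverses a PIPT benefit, and the favourable direction enlarges it. The result holds for the binary outcome under extreme assignment. It is not shown for the Oswestry, and no non-response rate is given for the medical-record outcomes.

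A reader might also infer that item 3 cannot address robustness at all. That too goes beyond the text. Extreme assignment gives valid bounds, but they are too wide to help here. How the investigators would report such a result is not in the documents.

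The 40% is a planning allowance, not an observed rate, and its split by arm is not stated. A better response rate alone would not change the conclusion, given the 9-11% threshold. Multiple imputation and the baseline comparison are useful, but neither examines non-ignorable missingness.

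**Conclusion.** Item 3 is under-specified. On its natural reading for the first primary outcome it is close to uninformative: the bounds are 80 points apart against a planned effect of 10 to 12 points, and the adverse bound reverses every benefit possible at the planned control rate. This rests on opposite extreme values for all missing patients by arm and on 40% missing in each arm. The reversal of the planned effect needs only about 9-11% missing. For the Oswestry, the finding is only that the assigned values are undefined.

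The graded figures (significance lost at about 22-23% among PIPT non-responders, effect gone at 40%, in the 25% vs 15% case) illustrate what a better-defined check would deliver. They depend on the effective sample size and on GBC non-responders matching GBC responders, and they leave out the extra variance from multiple imputation.

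**What to change.** Redefine item 3 as a delta-adjusted (pattern-mixture) tipping-point analysis built on the multiple imputation already planned:
- For chronic LBP, shift the imputed log-odds for non-responders, separately by arm, over a grid fixed in advance. Odds ratios from 1 to 5 would include the points where the effect vanishes under both planning scenarios (3.8 and 4.2).
- For the Oswestry, shift the imputed score by arm over a stated range of points.
- Report the shift at which each primary conclusion changes, both loss of significance and loss of the effect, and say how it will be interpreted.
- Keep the extreme bounds as a labelled supplement, with the assigned values and both directions defined.
- State whether and how item 3 applies to the secondary outcomes, which the section currently includes.

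The cost is SAP wording and modest programming on the existing imputations. Design, sample size and data collection do not change. The small downside is that the team must commit to a range of shifts before seeing the data by arm.

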## 9.2 Randomization, sample size and power – RCT cohort

- 9.2.1 **Randomization** will occur at the clinic level, which was chosen for the pragmatic reason that randomizing patients within a clinic would result in cross contamination of the interventions within the same clinic. The biostatisticians and the individuals conducting the 6-month assessments will be blinded to the randomization assignment to avoid bias in analyses and data capture.
- 9.2.2 **Sample size** is based on the first primary outcome of the transition rate to chronic LBP at month 6. We propose to enroll N=1860 high risk acute LBP patients. We are targeting an average of n=31 enrolled high risk patients per clinic ( $60 \times 31 = 1860$ ) to account for the variation in cluster sizes (assuming coefficient of variation=0.65) and 40% non-response rate at 6 months.
- 9.2.3 **Power:** With a total of 60 PCP clinics for randomization, m=30 clinics per intervention strategy and fixed n=10-14 completers per clinic for the 6-month assessment, we will have just over 80% power to detect a 40% reduction in transition to chronic LBP assuming the control arm has a transition rate of 25%-30% and the intraclass correlation is 0.05, which is an upper bound for what has been observed in other cluster randomized trials with respect to either pain or LBP. Assuming that low and medium risk subjects with acute LBP have an expected 20% transition to chronic and using data on obesity and smoking rates based on national surveys, depression rates based on prevalence rates reported in primary care, and proportions of underserved patients estimated from patient registries at each of the five regional sites, the planned sample size for the observational cohort is sufficient to detect at least a 30% relative difference (6% absolute difference) from 20% with powers ranging from 79% to 87%. The study would have 65% power to detect a 40% relative or 8% absolute difference (hypothesized increased rate of transition) for the depression subgroup.
- 9.2.4 **Treatment assignment procedures:** Detecting an interaction effect the same size as the overall intervention effect would require a four-fold increase in the effective sample size (more clinics and patients accounting for clustering), which is not feasible. There will be sufficient power to detect stronger intervention effects in some *a priori* defined subgroups at the participant level (smoking, depression, obesity, lower SES) if the cohort is evenly split.
- 9.2.5 **Analysis of randomization:** Distributions of baseline characteristics for clinics and patients will be compared between the study arms to assess effectiveness of the randomization, and statistical or clinical differences will be adjusted for in sensitivity analyses. All analyses for treatment group comparisons will use an intention-to-treat approach and results will be reported using the CONSORT extension to cluster randomized trials. This approach is highly pragmatic per the PRECIS-2 primary analysis domain.

### 9.3 Randomization, sample size and power – observational cohort

- 9.3.1 **Randomization** is not applicable to the observational cohort because moderate and low risk patients will not receive the PIPT intervention.
- 9.3.2 **Sample size** is again based on a total of 60 PCP clinics. An average of n=115 patients will be enrolled per clinic, for a total sample of N=6,900 low or medium risk acute LBP patients.
- 9.3.3 **Power:** The sample size will allow precise determination of 1) the transition rates for low risk and medium risk acute LBP who receive GBC; 2) differences between low/medium risk patients receiving GBC in the observational cohort and high risk patients receiving GBC in the intervention group; and most importantly, 3) differences among low/medium risk patients due to specific subgroup characteristics, in particular patients who are underserved, obese, depressed, or smokers. Of the three objectives, the subgroup analyses require the greatest sample size, and therefore will be described in detail here.

For the purposes of the calculations, from the literature it is assumed that low and medium risk subjects with acute LBP have an expected 20% transition to chronic. Data on obesity and smoking rates are based on national surveys. Depression rates are based on prevalence rates reported in primary care. Proportions of underserved patients are estimated from patient registries at each of the five regional sites. For the underserved, obesity, and smoking subgroups, the given sample sizes in Table 3 would be ample enough to detect at least a 30% relative difference (6% absolute difference) from 20% with powers ranging from 79% to 87%. The study would have 65% power to detect a 40% relative or 8% absolute difference (hypothesized increased rate of transition) for the depression subgroup.

**Table 3: Power** at a significance level of 0.05 to detect the specified % absolute and relative differences from a 20% chronic transition rate based on a two-sided Z-test adjusted for clustering within clinic (ICC=0.01) among 60 clinics, N=6900 enrolled and conservatively 60% response rate at 6 months in the low or medium risk population (adjusting for design effect and nonresponse N=2464).

| Subgroups (N)               | 25% relative difference
(5% absolute difference) | 30% relative difference
(6% absolute difference) | 35% relative difference
(7% absolute difference) | 40% relative difference
(8% absolute difference) |
|-----------------------------|---|---|---|---|
| Underserved (n=665 of 2464) | 74  | 87  | 95  | 98  |
| Obesity (n=640 of 2464)     | 73  | 86  | 94  | 98  |
| Depression (n=184 of 2464)  | 33  | 44  | 54  | 65  |
| Smoking (n=493 of 2464)     | 64  | 79  | 89  | 95  |

## 9.4 Outcomes

- 9.4.1 **Primary outcome 1:** To test the effect of the intervention on preventing the transition from acute to chronic LBP (**PA1**), the study team will compare the rates of transition to chronic LBP at 6 months, based on the results of the 6 month Chronic LBP Questionnaire, between enrolled patients at intervention clinics and enrolled patients at comparator clinics. This comparison will be conducted for high risk patients at 6 months (**PA1**) as well as low and medium risk patients (**SA4**) and specific subgroups (**SA5**).
- 9.4.2 **Primary outcome 2:** To test the effect of the intervention on improving patient-centered outcomes of back-related function (**PA2**), the study team will compare changes in the Oswestry scores from baseline to 6-month assessment between enrolled patients at intervention clinics and enrolled patients at comparator clinics. This comparison will be conducted for high risk patients at 6 months (**PA2**) as well as low and medium risk patients (**SA4**) and specific subgroups (**SA5**).
- 9.4.3 **Secondary outcomes:** To test the effects of the intervention on reducing medical resource utilization (**SA3**) the study team will compare LBP-related medical resource utilization data for enrolled patients at intervention clinics and enrolled patients at comparator clinics for a period of 12 months. This comparison will be conducted for high risk patients (**SA3**) as well as low and medium risk patients (**SA4**) and specific subgroups (**SA5**). The medical resource utilization data will be identified and categorized using Healthcare Common Procedure Coding System (HCPCS) Level 1 (CPT-4) and 2, and ICD-10 codes. These data will be used to evaluate the frequency, intensity and composition of services received within the participating PCP/PT practices as well as care delivered in other community practices and facilities. The study team will investigate evaluation & management services (PCP & specialist), diagnostic testing, rehabilitation services, and medical procedures. Furthermore, the study team will also capture prescribing patterns for key drug classes commonly used for LBP management such as non-steroidal anti-inflammatory drugs (NSAIDs), acetaminophen (Tylenol), opioid analgesics, skeletal muscle relaxants, antidepressants (e.g., tricyclic antidepressants and duloxetine), and drugs for neuropathic pain (e.g., gabapentin).

## 9.5 Data analyses

- 9.5.1 **Primary outcome 1:** This initial analysis (**PA1**) will use a generalized linear mixed model with a logit link controlling for block set (see Randomization) and a fixed effect for intervention accounting for the cluster RCT design with a random clinic effect. Primary analyses will also adjust for patient characteristics (maladaptive pain coping behaviors such as catastrophizing and fear avoidance, functional impairment as measured by the Oswestry, and presence

of psychiatric comorbidities), as these have been associated with higher transition to chronic LBP. The intraclass correlation coefficients will also be estimated and reported for all outcome measures to assess the assumptions for sample size analyses and also for future investigations using similar designs and outcomes. Analysis for the secondary aims (**SA4** and **SA5**) will be largely descriptive assessing the proportion of patients who transition to chronic LBP among the low and moderate risk observational cohort. The proportion and confidence interval will be estimated using generalized linear models adjusting for clustering.

- 9.5.2 **Primary outcome 2:** This aim (**PA1**) will be analyzed using contrasts from a linear mixed models analysis for 6-month back-related function (Oswestry) controlling for baseline Oswestry and the block set (see Randomization). The intervention will first be explored by time interaction, and then proceed to a main effects model with only group and time. For the secondary aims (**SA4** and **SA5**) patient-centered outcomes, such as functional status, would use general linear models if deemed appropriate based on normality assumptions. If normality is hugely violated, a cutpoint for 'response' will be applied.
- 9.5.3 **Secondary outcome:** Analyses of health care utilization data (**SA3**) will use generalized linear mixed models with the distribution determined by the type of data but still controlling for the cluster randomized trial design by having random effects for clinics. Logit link (binary distribution) will be used for health care outcomes, such as surgery, that are dichotomous (Yes/No) variables. For outcomes resulting in count data over the time frame such as number of outpatient visits for back pain, hospitalizations or ER visits, Poisson or negative binomial distribution with log link will be used to compare the event rates controlling for the period of follow up. The secondary aims (**SA4** and **SA5**) would use a similar approach.

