## 3.2 Randomization

The study will be conducted in five distinct US geographical areas in each of which a minimum of 12 primary care clinics will be participating and enrolling patients. The unit of cluster randomization will be the primary care clinic site. Thus, in one geographical area, six PCP clinics will be randomized to the GBC arm and six to the GBC+PIPT arm. The unit of randomization and analysis is a cluster because the intention is to enhance the application of a stratified approach to treating LBP in primary care environments as a whole while minimizing contamination. When randomization at the individual level was considered, it was found to be impractical and susceptible to selection bias and contamination.

The randomization for each study site will be conducted by the study biostatistician and will be stratified by two factors: Total Back Pain Encounters (Factor 1) and % Medicaid/Self-Pay (Factor 2). First, the clinics will be ordered by Factor 1 and divided into subgroups (blocks). Clinics in each block will then be further ordered by Factor 2, and randomly assigned to either group A or group B, making sure that the two groups would be balanced in terms of both Factor 1 and Factor 2.

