### 3.4 Study population and sites

The target population for this study will be adult patients who present to primary care physicians (i.e., internal medicine, family practice, and geriatric medicine physicians) with a primary complaint of LBP. Patients will be recruited from health systems in five regional areas that surround: 1) Pittsburgh, PA (UPMC); 2) Boston, MA (Boston Medical Center); 3) Baltimore, MD (Johns Hopkins Medicine); 4) Charleston, SC (Medical University of South Carolina); and 5) Salt Lake City, UT (Intermountain Healthcare). Within the individual regional areas, primary care clinics have been identified that represent community-based PCP clinics. In all instances, there are more potential sites than are required for successful completion of the trial, which will allow flexibility in the randomization scheme and alternatives should there be individual PCP-clinic recruitment shortfalls. This large, nation-wide group of clinics across five different health systems provides a high level of pragmatism for the PRECIS-2 organizational domain because the systems will be variable with regards to provider expertise, resources, and organizational structure.

Certain patient subgroups are of particular interest (**SA5**) given greater risk for poorer LBP outcomes as demonstrated in observational cohort studies. Adequate enrollment will be assured to have statistical power to conduct subgroup analyses of patients with lower socioeconomic status (using insurance as a proxy) and the comorbid conditions of smoking, depression, and obesity. Identification of subgroups will be based on information obtainable in the EMR. The participating primary care clinics will be sampled to reflect gender, race, and ethnicity proportions of the population being served at the recruitment sites.

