### Baseline sociodemographic variables

- Sex
- Race
- Hispanic ethnicity
- Date of birth
- Height
- Weight
- Body mass index
- Tobacco use
- Comorbid conditions
- Insurance status

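### Neither primary model names clinic % Medicaid/Self-Pay, the second factor that constrains the clinic randomization; the likely cost is some lost power, not bias

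*Combined protocol and SAP*

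**What the plan says.** Section 3.2 (Randomization) is carried out separately for each study site and uses two clinic-level factors: total back pain encounters (Factor 1) and % Medicaid/Self-Pay (Factor 2). Clinics are first ranked on Factor 1 and cut into blocks. Then: "Clinics in each block will then be further ordered by Factor 2, and randomly assigned to either group A or group B". The section also requires the arms to come out even on the two factors. Both factors therefore restrict which allocations are possible, but only Factor 1 defines a block.

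Section 9.5.1 specifies a logit mixed model for PA1, "controlling for block set (see Randomization) and a fixed effect for intervention accounting for the cluster RCT design with a random clinic effect". It adds patient covariates: "Primary analyses will also adjust for patient characteristics (maladaptive pain coping behaviors such as catastrophizing and fear avoidance, functional impairment as measured by the Oswestry", plus psychiatric comorbidity. Section 9.5.2 specifies a linear mixed model for PA2 with baseline Oswestry and the same block set. Neither section names Factor 2, and the term *block set* is defined nowhere.

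Section 3.4 describes certain patient subgroups, lower socioeconomic status (by insurance) among them, as of interest "given greater risk for poorer LBP outcomes as demonstrated in observational cohort studies". Section 9.2.5 adjusts for baseline differences between arms only in sensitivity analyses.

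**The concern.** The usual principle is that the analysis should reflect the restrictions in the randomization. When arms are forced to balance on a prognostic factor, the treatment estimate varies less from one allocation to another. A model without that factor does not know this. It leaves the factor's variance in the residual between-clinic variance, so the standard error is too large, the true type I error falls below nominal, and power is given away.

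The planned power for PA1 is only just over 80% (section 9.2.3), so a few points matter. The sensitivity rule in 9.2.5 is unlikely to help, because a factor balanced by design should show little difference between arms. There is also a reproducibility problem: with *block set* undefined, two statisticians could fit different primary models from the same text.

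**Working it through.** **Inputs from the plan.** 60 clinics, 30 per arm; 10 to 14 completers per clinic (fixed size); control rate 25% to 30%; 40% relative reduction; ICC 0.05; 31 enrolled per clinic with 40% non-response, so 31 × 0.6 = 18.6 completers on average (section 9.2). Two-sided 0.05 is stated only for the observational cohort (Table 3) and is assumed here for the RCT.

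**Inputs assumed.** The share R² of between-clinic variance that Factor 2 explains within blocks, which the documents do not give; volume blocks of four clinics; allocation in adjacent pairs on the Factor 2 ordering.

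**1. The plan's own figure.** Effective patients per arm = 30n / (1 + (n − 1) × ICC), then a two-proportion test.
- 25% vs 15%, n = 14: 420 / 1.65 = 254.5 per arm; power 80.7%.
- 30% vs 18%, n = 10: 300 / 1.45 = 206.9 per arm; power 81.8%.

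The stated figure of just over 80% is reproduced.

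**2. Formula power with Factor 2 in the model.** Replace ICC by 0.05 × (1 − R²).

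| R² | 25% vs 15%, n = 14 | 30% vs 18%, n = 10 |
|---|---|---|
| 0 | 80.7% | 81.8% |
| 0.10 | 82.3% | 83.0% |
| 0.25 | 84.6% | 84.8% |
| 0.50 | 88.4% | 87.7% |

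The gains are 1.2 to 1.6 points at 0.10, 3.0 to 3.9 at 0.25, and 5.9 to 7.7 at 0.50.

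**3. Simulation of the restricted randomization.** Clinic-level analysis, 14 completers per clinic, base rate 0.25, absolute effect 0.10, 6,000 runs per scenario.

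| R² | Type I error, block only | Type I error, block + Factor 2 | Power, block only | Power, block + Factor 2 |
|---|---|---|---|---|
| 0 | 5.0% | 4.8% | 72.6% | 72.0% |
| 0.25 | 4.4% | 5.3% | 73.4% | 76.8% |
| 0.50 | 3.6% | 4.7% | 73.3% | 81.5% |

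Monte Carlo error is about 0.3 points for type I error and 0.6 for power. Power sits below the formula because this is a clinic-level t-test with the 25% variance in both arms, so only the differences between models should be read: about 3 points at 0.25 and 8 at 0.50. At R² = 0 the two models agree within simulation error.

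A second simulation with 18.6 completers per clinic gives standard-error reductions of 2% / 7% / 13% at R² = 0.10 / 0.30 / 0.50. Power goes from about 80–81% to 81% / 85% / 89%, and type I error without Factor 2 is 4.8% / 4.2% / 3.3%.

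**4. Hand check of those reductions.** The between-clinic share of the variance of a clinic mean is 0.05 / (0.05 + 0.95/18.6) = 0.495. The standard error ratio is √(1 − 0.495 R²) = 0.975 / 0.923 / 0.868, that is, cuts of 2.5% / 7.7% / 13.2%. These agree with the simulation apart from the small cost of the extra degree of freedom.

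**5. What shrinks the effect.**
- Lower ICC. At an assumed 0.02 the share is 0.02 / (0.02 + 0.98/18.6) = 0.275, so the cuts are 1.4% at R² = 0.10 and 4.2% at 0.30. Simulated power moves only from about 92% to 92–93%.
- Factor 2 varying between sites or blocks. The block term already absorbs that part. If half of it lies there (assumption), the simulated cut at ICC 0.05 is about 1% at R² = 0.10 and 3.5% at 0.30, worth about 0.3 and 2 points of power.

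**The case against.** The strongest reply has four parts.

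*The block set may already cover Factor 2.* Section 9.5 points back to a two-factor procedure, so the term could mean the sets formed by volume block and Factor 2 order. This stands as a possibility and limits the certainty of the point. But section 3.2 uses the word block only for the volume grouping, and the ambiguity itself needs removing.

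*The prognostic link is stretched.* Section 3.4 speaks of patients' socioeconomic status, not of a clinic's payer mix. This stands: clinic-level prognosis is an inference, though a reasonable one, since the sponsor chose Factor 2 to constrain the randomization.

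*The size may be small.* Section 9.2.3 calls ICC 0.05 an upper bound, no document supports R² of 30% to 50%, and the PA1 patient covariates may carry part of any socioeconomic effect. The calculations contain no patient covariates, use equal clinic sizes although section 9.2.2 assumes a coefficient of variation of 0.65, and work on clinic proportions instead of the logit mixed model. All of this stands.

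*Stronger readings fail.* A reader might infer that the models adjust for volume block and nothing else; PA1 has three kinds of patient covariate and PA2 has baseline Oswestry. A reader might infer bias or a raised false-positive rate; balance by design rules out the first, and the simulated error rates without Factor 2 are at or below nominal. A reader might also conclude that patient insurance must enter the primary models. It is not a randomization factor, no gain from it has been quantified, and the plan already uses it in the subgroup analyses (1.2.4, 9.1.12) and in comparing complete with missing cases (9.1.15).

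**Conclusion.** The point holds in a limited form. Of the two factors that constrain the allocation, Factor 2 is named in neither primary model, and the term that might carry it is undefined. If Factor 2 is prognostic at clinic level, the PA1 test is mildly conservative. At ICC 0.05 the loss is about 1 point of power at R² = 10%, 3 to 5 points at 25% to 30%, and up to about 8 points at 50%, the last being an upper case without support in the documents. If Factor 2 explains nothing within blocks, the omission costs nothing. The same reasoning applies to PA2, but its size is not computed because section 9.2 bases the sample size on PA1 alone. The figures rest on the assumed R², blocks of four and pairwise allocation. This is a low-cost improvement in precision and clarity; it does not threaten the validity of the primary comparison.

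**What to change.** In section 9.5.1, define the block set as the site-specific Factor 1 block from section 3.2, and add clinic % Medicaid/Self-Pay as a fixed effect, using the continuous value that was used at randomization. Make the same change in 9.5.2, so that both primary models carry both randomization factors, and settle it before the statisticians are unblinded.

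The cost is a sentence in each section and one degree of freedom per model. No new data are needed, because the clinic values had to exist for the randomization. A patient-level insurance covariate is not part of this change.
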